Effect of the adjunction of the Double Trunk Mask above standard
nasal cannula during acute hypoxia
5 March 2018

Study Protocol and Statistical Analysis Plan

Study Design

This is a single-center, randomized, blind investigator, 2-way crossover study design. Enrolled participants had hypoxia being treated at Intensive Care Unit associated with a hospital in Hornu (Epicura).

The study consisted of two intervention periods separated by a washout period of 30 minutes. (Figure 1)

The objective of the study is to determine whether adjunctive mask of our design (Double Trunk Mask - DTM) has an effect on increasing arterial pressure in Oxygen (PaO₂) diagnosed with hypoxia. The protocol and informed consent documents were reviewed and approved by a recognized ethics review board at the study facility. The study was performed in accordance with the Declaration of Helsinki.

Participants

Inclusion Criteria:

Regardless of gender, at least 18 years of age and diagnosed with Hypoxia (PaO₂/FiO₂ < 380 mm Hg), dyspnea, respiratory rate (RR) ≥ 25 CPM, PaCO₂ ≤ 45 mmHg, patient with an arterial catheter and without hemodynamic instability, Glasgow Coma Scale ≥ 12/15, written consent. Participants were also required to have a sufficient level of education to understand study procedures and be able to communicate with site personnel.

Exclusion Criteria

Patients were excluded if they Hypercapnia (> 45 mm Hg with respiratory acidosis), COPD, pulmonary fibrosis, hypoventilation obesity syndrome, arterial pressure < 60 mm Hg or treatment by epinephrine > to 0,1 gamma/kg/minute, deterioration of awareness (Glasgow scale < or = 12), acute confusional state.

Participants were randomized in a 1:1 ratio to receive either classical oxygenation with nasal cannula (NC) for 20 minutes or NC with an adjunctive of a Double Trunk Mask.

Effect of the adjunction of the Double Trunk Mask above standard
nasal cannula during acute hypoxia
5 March 2018

Primary Endpoints

The primary endpoint was the change of PaO₂.

Sequence (Figure 1): The patient should be placed in semi-seated (position at 45 °)

Patient will be oxygenated with classical nasal cannula. Oxygen flow rate will be adjusted to obtain a Saturation in oxygen > at 90%.

1. Arterial gazometry will be taken after 20 and 60 minutes with NC.
2. The clinician will associate the Double Trunk Mask (DTM) with the same parameters of the nasal cannula. Arterial gazometry will be performed after 20 and 60 minutes after placement of DTM.
3. After the withdrawal of DTM, arterial gazometry will be performed after 20 and 60 minutes

Statistical Analysis

All participants who received this intervention and completed two phases of study were included in the efficacy analysis.

A sample size of 20 participants was needed to provide 90% power to detect a 10 mm Hg difference in PaO₂. ANOVA for repeated measures followed by a post hoc test will be used to compare the difference between participants receiving (CN + DTM) and CN alone.

The test was performed with a significance level of 0.05 (two-sided). Statistical analyses were carried out using SigmaPlot software version 12.0 (Systat Software Inc. UK).

Adverse Event Assessment

Safety was assessed by the number of participants with adverse events (AEs). AEs were collected by systematic assessment using terms from the Medical Dictionary for Regulatory Activities (MedDRA), version 11.1 in participants who received one or more doses of intervention. Adverse events during washout were not collected.

Figure 1

Effect of the adjunction of the Double Trunk Mask above standard nasal cannula during acute hypoxia
5 March 2018

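### The stated 1:1 randomised two-period crossover and the single written order (NC, then DTM, then withdrawal) contradict each other, and the visible SAP text does not reconcile them

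*Protocol*

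**What the plan says.** Study Design (protocol) states "This is a single-center, randomized, blind investigator, 2-way crossover study design" and "The study consisted of two intervention periods separated by a washout period of 30 minutes". The allocation sentence under Participants reads "Participants were randomized in a 1:1 ratio to receive either classical oxygenation with nasal cannula (NC) for 20 minutes", with NC plus DTM as the alternative.

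The Sequence under Primary Endpoints starts the patient on NC and then lists three steps:

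- Step 1: "1. Arterial gazometry will be taken after 20 and 60 minutes with NC".
- Step 2: "2. The clinician will associate the Double Trunk Mask (DTM) with the same parameters of the nasal cannula". Then: "Arterial gazometry will be performed after 20 and 60 minutes after placement of DTM".
- Step 3: "3. After the withdrawal of DTM, arterial gazometry will be performed after 20 and 60 minutes".

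The primary endpoint is given only as the change in PaO₂, with no reference stage or time point.

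The SAP's Statistical Analysis section limits the efficacy analysis to participants who finish two phases. It names a repeated-measures ANOVA with an unspecified post hoc test. It gives no period or sequence term, no contrast and no time point. In both documents the Adverse Event Assessment excludes events during a washout. The protocol cites Figure 1 for both the two-period design and the Sequence, and the SAP also ends with it, but it is not shown in the text reviewed.

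**The concern.** A randomised two-way crossover needs two orders, NC first and DTM first. Randomising the order is what separates treatment from time. The numbered steps contain only NC first, so under them a 1:1 allocation would assign nothing.

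The patients are acutely hypoxic and in intensive care, so PaO₂ may move over an hour or two through recovery, deterioration or other treatment. In a fixed order that movement enters the NC-to-DTM difference directly. Upward drift can mimic a DTM effect, and downward drift can hide one.

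At stake is whether the result may be called a randomised effect at all. The model, the analysis set and the adverse-event window, which leaves out a washout that the steps never place, all depend on the answer.

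**Working it through.** **1. The two descriptions side by side**

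| Item | Study Design and Participants | Sequence |
|---|---|---|
| Order | 1:1 randomised | NC, DTM, withdrawal only |
| Periods | two | three measured stages |
| Washout | 30 minutes | no step |
| Time on NC | 20 minutes | gases at 20 and 60 minutes |

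The rows do not agree. The SAP's two phases do not say which of the three stages are meant.

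**2. What each design can estimate**

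Let the stage means be NC = μ, DTM = μ + π₂ + τ, withdrawal = μ + π₃, where τ is the DTM effect and π₂, π₃ are time effects.

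- Step 2 minus step 1 is π₂ + τ, so τ is aliased with time.
- All three stages with free time effects: 4 columns, rank 3. τ is not estimable.
- Linear drift (π₂ = δ, π₃ = 2δ), equal spacing and no carryover: DTM minus the mean of the NC stages is τ + δ − (0 + 2δ)/2 = τ. Adding a carryover term again gives 4 columns, rank 3.
- Two randomised sequences with sequence, period and treatment terms: 4 columns, rank 4. τ is estimable if there is no carryover.

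**3. Size under a fixed order (illustration)**

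From the documents: n = 20, 10 mm Hg, 90% power, two-sided 0.05. They give no SD, so 20 cannot be reproduced, only back-solved. For a paired t test (19 df, critical value 2.093), 90% power needs 10/SD = 0.7645. Hence SD of the difference = 13.08 and SE = 13.08/√20 = 2.93.

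The drift values are assumed, with one gas per stage and no true effect (noncentral t):

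| Drift | Drift/SE | Unadjusted | Bonferroni, 0.05/3 |
|---|---|---|---|
| 3 mm Hg | 1.03 | 16.4% | 7.5% |
| 5 mm Hg | 1.71 | 36.8% | 20.9% |

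For 5 mm Hg and an SD of 10 to 20, the range is 56% to 19% unadjusted and 37% to 9% with Bonferroni. In the other direction, a true 10 mm Hg effect with 5 mm Hg downward drift leaves 10 − 5 = 5 mm Hg, detected in the same 36.8% of trials instead of 90%.

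**4. Randomised order, 10 + 10, 18 df, same SD**

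Power is 89.8% without carryover. If 50% of the effect carries into the next NC period, the NC-first difference is 10 and the DTM-first difference is 10 − 5 = 5. The mean is 7.5 mm Hg and power is about 68%.

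**5. Fixed order, possible contrasts (independent stage errors assumed)**

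Stage SD = 13.08/√2 = 9.25. DTM minus the mean of both NC stages has SD 9.25 × √1.5 = 11.33 and 96.3% power at 10 mm Hg.

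- A rise of 5 or 10 mm Hg that plateaus before the DTM gas leaves bias 5 − 5/2 = 2.5 or 10 − 10/2 = 5, hence 15.5% or 46.6% false positives.
- 50% carryover shrinks 10 to 10 − 5/2 = 7.5 mm Hg, with 80.2% power.
- Requiring DTM to be significantly above each NC stage gives, by simulation, 2.0% or 2.6% under the same plateaus (the second is within simulation error of its 2.5% ceiling). Power is 83%, or 36% with 50% carryover.

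**The case against.** The strongest objection is Figure 1. It is cited for both the design and the Sequence, and it may show two orders and the washout. This stands as a limit on the conclusion. A reader might infer that the trial was not randomised, or that its result is only drift; the documents support neither. The tenses are mixed (the design in the past, the steps in the future), so even the state of conduct is unclear. But a figure showing two orders would itself conflict with the numbered steps, so the text needs correcting either way.

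Step 1 might be a common run-in, or step 3 might be the washout. No passage says either. If step 3 were the 30-minute washout, its 20-minute gas would fall inside it, but that is only conjecture.

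The withdrawal stage and the two NC gases give some protection: they can show drift and a fall back after withdrawal. That is true, and the ANOVA may include them, but neither document names a contrast that uses them, and finishing two phases does not require the third stage.

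The percentages rest on an assumed drift and a back-solved SD, and use one gas per stage where the protocol takes two. That also stands: they illustrate scale only. Nor do the documents make any one fixed-order contrast the right primary analysis; each has a clear weakness. The 20- against 60-minute mismatch is a separate wording conflict from the order, but the same revision should settle it.

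**Conclusion.** The point holds as a contradiction in the text, with high confidence, and must be fixed. The stated randomised two-period crossover with washout and the single written three-stage order cannot both be right, and the visible SAP text does not choose between them.

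Aliasing of DTM with time is conditional on the numbered steps being followed. It is complete for step 1 against step 2, and only partly relieved by step 3, under linear drift, equal spacing and no carryover. On that condition, a 5 mm Hg drift would mean roughly 37% false positives unadjusted or 21% with Bonferroni, given n = 20 and an SD of 13.1 mm Hg. The documents supply neither the drift nor the SD.

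**What to change.** **Required.** Establish from Figure 1 and the allocation records which order was or will be used. Then make the design statement, Sequence (period lengths and washout), analysis set and SAP agree with it.

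- *Order randomised:* write out both sequences and the washout, say what the step 3 gases are for, and fit treatment with period and sequence terms. State that about 90% power at n = 20 assumes no carryover.
- *Order fixed:* remove the claims of randomisation, 1:1 allocation and two-way crossover. Report a non-randomised before/during/after study, and say that its NC-DTM difference cannot be fully separated from time.

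**Optional, fixed order only.** Report DTM against each NC stage and against their mean, at one time point common to all stages. State that the mean contrast removes only linear drift with equal spacing and no carryover, and that requiring DTM to exceed both stages guards against a plateau at a cost in power (83% against 96%). Label any contrast chosen after data exist as post hoc.

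**Cost.** Rewording of both documents, with no extra patients or gases. If the order was fixed, the claim becomes weaker. If patients have already followed the steps, relabelling them as a crossover would misdescribe the trial. Moving to a randomised order would change conduct, not only wording.

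### The planned analysis names no primary DTM–NC contrast and no period or sequence term for a stated randomised 2-way crossover, so several gas pairs could supply the primary result

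*Protocol*

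**What the plan says.** Study Design in the protocol calls the trial a randomised 2-way crossover and adds: "The study consisted of two intervention periods separated by a washout period of 30 minutes". Under Participants, patients are randomised 1:1 "to receive either classical oxygenation with nasal cannula (NC) for 20 minutes" or NC with the mask. The endpoint is given only as PaO₂ change: "The primary endpoint was the change of" PaO₂, with no time point and no reference gas.

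The numbered steps under Primary Endpoints read differently. Step 1: "Arterial gazometry will be taken after 20 and 60 minutes with NC". Step 2 adds the mask and takes gases at the same two times. Step 3: "After the withdrawal of DTM, arterial gazometry will be performed after 20 and 60 minutes". That makes three phases with two gases each, six gases in all, written in one order.

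Statistical Analysis in the protocol has one sizing sentence, "A sample size of 20 participants was needed to provide 90% power to detect a 10 mm Hg difference", and a two-sided 0.05 level. It has one method sentence, "ANOVA for repeated measures followed by a post hoc test will be used to compare the difference between participants receiving" mask plus cannula or cannula alone. The analysis set is given as: "All participants who received this intervention and completed two phases of study were included in the efficacy analysis". The SAP repeats these sentences, with the method sentence in the past tense. Neither document gives an SD, names the post hoc test or lists model terms.

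**The concern.** Two things are left open that the design needs settled.

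The first is the primary contrast. A DTM gas at 20 or at 60 minutes can be set against NC before the mask, the gas after withdrawal, or both. Each choice fits the text, and the choice could be made after the results are seen. The stated power is tied to none of them.

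The second is the model. In a two-period crossover, anything that shifts PaO₂ between the first and second period moves the DTM-minus-NC difference up in one sequence and down in the other. With balanced order the estimate stays unbiased. Without a period term, however, the shift is counted as noise and power is lost. A period term removes that loss, and none is specified.

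**Working it through.** 1. The plan's own figure. The inputs given are N = 20, a difference of 10 mm Hg, two-sided 0.05 and 90% power (Statistical Analysis, both documents). The SD is not given, so 20 cannot be derived forward. Solving backward for one paired t test: power = P(|T| > t₀.₉₇₅,₁₉), where T is noncentral t with 19 df and noncentrality 10·√20/SD. The critical value is 2.093. Power equals 0.900 at SD = 13.08, where the noncentrality is 10 × 4.472 / 13.08 = 3.42. An SD of paired differences of about 13.1 mm Hg or less therefore supports the stated 90%. At an assumed SD of 15 or 20 the power would be 80.7% or 56.5%. The documents do not say which applies. The steps below use 13.08.

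2. Number of candidate contrasts. Matching on time, DTM can be compared with pre-mask NC at 20 and at 60 minutes (two pairs) and with the post-withdrawal gas at 20 and at 60 minutes (two more). That gives four matched pairs from six gases.

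3. Period effect ignored. Let p be the second-period minus first-period shift (assumed), with 10 patients per sequence.
   - The DTM-minus-NC difference is 10 + p in one sequence and 10 − p in the other, so the overall mean remains 10.
   - The expected sample variance of the 20 differences becomes 13.08² + (20/19)·p². The apparent SD is 14.05 for p = 5 and 16.62 for p = 10.
   - The mean difference needed for significance is 2.093 × SD/√20: 6.12 for p = 0, 6.58 for p = 5, 7.78 for p = 10.
   - The true standard error of the mean is still 13.08/√20 = 2.925. A normal approximation, P(Z > (threshold − 10)/2.925), gives about 91%, 88% and 78%. Simulation of the t test gives 90%, 87% and 77%.

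4. Period effect adjusted. With a period term the error df falls from 19 to 18. Power is 89.8% whatever the value of p.

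5. False positives from choosing among pairs. Assume no treatment or time effect and equal correlation between gases.
   - No ANOVA gate and no adjustment: for two matched pairs, 1 − 0.95² = 9.75%, or about 10%. For four matched pairs, independence would give 1 − 0.95⁴ = 18.5%; because the pairs share DTM gases, simulation gives about 17%.
   - Unadjusted tests run only after a significant overall F: about 3.5% (four gases), 2.6% (six gases, pre-mask NC only) and 4% (six gases, either reference).
   - Gate plus Bonferroni over all pairs: at most 1.5%.

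**The case against.** The strongest reply is that the harm is smaller than it looks. The wording, an ANOVA followed by a post hoc test, is most naturally read as a gate. On that reading the any-pair error stays below 5% even with unadjusted tests, and many post hoc tests carry their own adjustment. This largely stands. A reader might infer that the plan inflates the type I error, but the documents support that only if the tests are neither gated nor adjusted. What remains is that the gate is not stated, the figure holds only when no gas differs from any other, and a gate does not say which pair is the primary result.

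A reader might also infer that 20 patients are too few. The documents do not show this: an SD of 13.1 mm Hg or less reproduces the 90%. Nor do they specify an all-pairs correction that would erode power. Even under Bonferroni over all pairs after a significant ANOVA, at least one of the four matched pairs is significant in 95.7% of trials if DTM adds 10 mm Hg at both its gases.

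A third tempting reading is that order was fixed, so that DTM is confounded with time. The numbered steps do read that way, but Study Design and Participants say randomised, 1:1 and crossover. The steps may describe one sequence only, and Figure 1, which they cite, is not available here. The two descriptions need reconciling; a fixed order is not established.

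**Conclusion.** The concern holds as an inexpensive improvement to the analysis. The written plan has no primary DTM–NC contrast and no period or sequence term, although it describes a randomised two-period crossover with up to four matched comparisons.

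The size is conditional. Power falls from 90% to 87% or 77% only if a period effect of 5 or 10 mm Hg exists, the paired-difference SD is 13.1 mm Hg, order is balanced, and period is left out. The 10–17% false-positive range applies only to ungated, unadjusted tests. The period effects are assumptions, and the SD is solved from the plan's own power statement. The missing SD and the unnamed post hoc test are gaps in reporting: they make the 90% uncheckable but do not show it to be wrong.

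**What to change.** First reconcile the crossover text with the numbered steps, including the 20-minute NC duration beside the 60-minute gases, and the two phases in the analysis set beside the three in the steps.

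Then, before any outcome data are examined:

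- Name one primary contrast, for example DTM minus NC at 20 minutes, the only duration that Participants attaches to the randomised comparison. This is a choice of analysis time and says nothing about how long each phase should last.
- If order is randomised, estimate the contrast from a crossover model with treatment, period and sequence terms and patient as a random effect, two-sided 0.05, with a 95% confidence interval.
- Make the 60-minute and post-withdrawal comparisons secondary with Holm adjustment. Keep post-withdrawal gases out of the two-period primary model unless they are the NC period of that sequence.
- If order proves to be fixed, say that DTM cannot be fully separated from time.
- State the SD behind the 90% and its source, and restate the power at N = 20 if that SD does not support it.

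The change of analysis needs no extra gases. It costs one degree of freedom (89.8% against 90.0% at SD 13.1), and the other comparisons lose confirmatory status. Whether 20 patients suffice depends on the SD, which this change does not settle. The documents mix past and future tense; if data have already been collected, the contrast must be labelled as not prespecified.

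### AEs in the 30-minute washout are not collected, so the only named safety measure can miss events there, including any that follow mask removal (minor)

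*Protocol*

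**What the plan says.** Protocol, Adverse Event Assessment, says: "Adverse events during washout were not collected". The SAP has the same sentence under the same heading. In both documents that section names one safety measure, a count of participants who had an AE, and says that AEs were gathered systematically. Neither document gives a reason for leaving out the washout, and no other visible text provides for recording AEs during it.

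The timing comes from the protocol:

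- Study Design: "This is a single-center, randomized, blind investigator, 2-way crossover study design", and "The study consisted of two intervention periods separated by a washout period of 30 minutes".
- Participants, randomization sentence: "Participants were randomized in a 1:1 ratio to receive either classical oxygenation with nasal cannula (NC) for 20 minutes". The alternative, cannula plus mask, has no duration there.
- Sequence, step 1: "Arterial gazometry will be taken after 20 and 60 minutes with NC".
- Sequence, step 2: "The clinician will associate the Double Trunk Mask (DTM) with the same parameters of the nasal cannula", then "Arterial gazometry will be performed after 20 and 60 minutes after placement of DTM".
- Sequence, step 3: "After the withdrawal of DTM, arterial gazometry will be performed after 20 and 60 minutes".

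The protocol cites Figure 1 both for the washout and for the Sequence. The figure is not in the text available to this review, which is not a fault of the plan.

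**The concern.** Participants are hypoxic, dyspnoeic ICU patients, and the study tests a device of the study team's own design. Safety rests on one count. A rule that removes a defined stretch of follow-up from that count can leave events out, and the time just after a device is taken off is time in which an AE could occur. The protocol itself treats the time after withdrawal as worth observing, since it plans two blood gases there.

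What is at stake is the completeness of the safety statement. A report that few or no participants had an AE would be silent about the washout, and a reader who missed the one-sentence exclusion would not know that.

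**Working it through.** **Plan's own figure.** There is none to reproduce on this point. The documents state no total study time, no percentage of time covered and no AE risk. The planned sample size of 20 (Statistical Analysis, both documents) is used below only as a multiplier.

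**Inputs.** Washout: 30 minutes, one per participant (Study Design). Period length: 20 minutes for cannula (randomization sentence), or at least 60 minutes per phase if the last planned gas is taken (Sequence, steps 1 to 3). Participants: 20 planned. The size of the safety population is not given.

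**Unrecorded time.** 20 × 30 = 600 participant-minutes.

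**Share of planned time per participant.** Where the washout is added to the phases, share = 30 / (sum of phase lengths + 30). Where it lies inside a phase, share = 30 / (sum of phase lengths).

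| Reading | Calculation | Share |
|---|---|---|
| Three 60-minute phases, washout added | 30/(60+60+60+30) = 30/210 | 14.3% |
| Three 60-minute phases, washout inside one | 30/(60+60+60) = 30/180 | 16.7% |
| Two 60-minute periods, washout between | 30/(60+30+60) = 30/150 | 20.0% |
| Cannula 20, mask 60, washout added | 30/(20+60+30) = 30/110 | 27.3% |
| Two 20-minute periods, washout between | 30/(20+30+20) = 30/70 | 42.9% |

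The first three rows are consistent with 60-minute gases in every phase and give 14% to 20%. The last row assumes a 20-minute mask period. No passage states that, and it does not fit the planned gas at 60 minutes after mask placement.

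**Which events are lost.** Taking the sentence as written:

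- Only AE begins and resolves in washout: the participant is not counted.
- AE begins in washout and continues into a later recorded period: unclear. The text does not say whether AEs are assigned by onset or recorded whenever present.
- Another AE occurs in a recorded period: the participant is counted anyway, so the count does not change.

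Each participant in the first group lowers the count by 1. With no AE risk in the documents, the size of that group cannot be estimated.

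**How many washouts follow the mask.** This depends on the order of interventions and on where the washout falls:

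- Randomized 1:1 crossover: 20/2 = 10 participants, 10 × 30 = 300 participant-minutes.
- Sequence order for everyone, washout before the mask: 0 participants, 0 participant-minutes.
- Sequence order for everyone, washout starting at mask withdrawal: 20 participants, 20 × 30 = 600 participant-minutes.

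In the last case 20 < 30 < 60, so the first post-withdrawal gas falls inside the washout and the second outside. A PaO₂ value would then be kept from time in which AEs are not recorded. The visible text does not settle which case applies; Figure 1 may.

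**The case against.** The strongest reply is that the exclusion is openly stated, identical in both documents, and defines a legitimate target: AEs while on an assigned intervention. That is a coherent choice, and the plan does not hide it. Disclosure tells a careful reader about the gap, though; it neither gives a reason nor closes it. The section also does not describe its measure as limited to on-intervention events, beyond the exclusion itself.

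Second, the past tense suggests that collection may already be over. If so, only chart recovery and a limitation statement remain. This stands, and the fix allows for it.

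Third, the percentages invite over-reading. A reader might infer that up to 43% of the safety data is lost. The documents do not support that: the figure needs an assumed mask duration, and a share of minutes is not a share of events. A reader might also infer that the count must be too low for everyone with an event in washout. That too goes beyond the text, because an event continuing into the next period could be recorded there.

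Fourth, the tension between a randomized order and the single listed Sequence is a different and larger matter. It limits how precisely the post-mask gap can be stated here but adds no weight to this point.

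**Conclusion.** The point holds as a minor one. Both documents exclude a 30-minute washout from the only named safety measure, and a participant whose sole AE begins and resolves there would go uncounted. The excluded time is about 14% to 20% of planned time if 60-minute gases are taken in every phase. The higher figure of 43% depends on two 20-minute periods, of which the text supports only the cannula one. Between 0 and 20 washouts follow the mask, depending on order and placement. Figure 1 may narrow that range, so missing information on placement is not claimed as a defect.

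A reader might infer that the rule makes the mask look safer than cannula. The documents do not show this: on a randomized crossover the washout would follow each intervention in about half the participants, and there is no AE risk from which to derive a difference. The number of missed events is unknown, and the PaO₂ analysis does not depend on AE collection.

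**What to change.** In both documents, replace the sentence on washout with:

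> AEs are recorded continuously from the start of the first intervention, through washout, to the end of study observation; AEs with onset in washout are included in the number of participants with AEs and also listed separately by the preceding intervention, without assuming causality.

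Define the end of study observation alongside it, since the visible text gives no end time for AE collection.

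If data collection is complete, keep the existing statement because it describes what was done. Recover washout events from ICU records where possible, label them as retrospective, and state that the safety conclusion does not cover the washout.

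Separately, reconcile the randomized crossover text with the fixed Sequence. The number of washouts that follow the mask can then be stated.

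Cost: systematic AE assessment is already in place, so this extends it by 30 minutes per participant. The downside is a few more AE entries and possibly a less favourable count. If collection is over, the cost is a check of about 20 charts and one limitation sentence.
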